6.5 Handling of Missing Data

The handling of missing data, if applicable, is discussed in Section [8.0](#) (Analysis Variables: Definitions, Derivations, Calculations and Conventions). Presentation of missing data is discussed in the relevant subsections of Section [9.0](#) (Statistical Analysis).

7.0 Objectives

7.1 Primary Objective

The primary objective of this study is to provide, under well controlled conditions, continued access to LCIG treatment to subjects who have already participated in an open label efficacy and safety trial with the same treatment (Study S187.3.003 or

Study S187.3.004), and in whom the need for such continuation is indicated, as confirmed by periodic evaluation, until the product is commercially available.

7.2 Secondary Objectives

To assess the long-term safety and tolerability of the LCIG therapeutic system by the following:

- Physical examination, including weight
- Neurological examination
- Vital signs
- Resting ECGs
- Clinical laboratory assessments including biochemistry, hematology, urinalysis, and special labs to monitor for vitamin deficiencies
- Concomitant medication usage
- Adverse event monitoring, including for the development of sleep attacks, melanoma, or excessive impulsive behavior
- Monitoring complications of the infusion device
- Tolerability assessed by number of subjects who complete the study

To assess the maintenance of efficacy using the following data collected from US subjects:

- Off time, On time with troublesome dyskinesia, and On time without troublesome dyskinesia as measured by the Parkinson's Disease Diary
- UPDRS total score, Parts I, II, III and IV scores, and dyskinesia item score
- PDQ-39 summary index and domain scores

8.0 Analysis Variables: Definitions, Derivations, Calculations and Conventions

8.1 Subject Disposition

8.1.1 Subject Samples

There will be three hierarchical subject samples of interest.

The "All Subjects Consented" subject sample will be used to summarize subject disposition and will consist of all subjects who:

- Gave their informed consent.

The Safety subject sample will consist of all subjects who:

- Were in the "All Subjects Consented" subject sample and
- Received at least 1 infusion of 3005 study drug

The Safety subject sample will be used for all analyses of safety unless noted otherwise.

The Efficacy subject sample will consist of all subjects who:

- Were in the Safety subject sample and
- Have at least 1 efficacy assessment in 3005

The Efficacy subject sample will be used for all analyses of efficacy unless noted otherwise.

For subjects enrolled in the United States, efficacy assessments were added with Protocol Amendment 4. To evaluate efficacy and safety in these subjects, analyses will be completed including only the subjects in the relevant subject sample who were enrolled in the United States (the "US Subset").

To evaluate the association between polyneuropathy events and vitamin deficiencies, additional analyses will be completed for the subset of subjects who experienced a TEAE coded to either the Standardized MedDRA Query (SMQ) of Peripheral Neuropathy – narrow search or Guillain-Barre Syndrome – narrow search (the "Narrow Polyneuropathy Subset").

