9.11.2 Clinical Laboratory Evaluation

All laboratory tests will be presented in System International (S.I.) units only, unless otherwise specified.

Subject Samples:	Tables	Safety sample
	Listings	All subjects consented
	Figures	Not applicable
Subgroups:		Not applicable
Abbreviation:		LB

Standard Presentations

- LBT001 For those variables with a PCS criterion (as defined in [Table 4](#)) the incidence of marked abnormalities per laboratory parameter will be presented. The percentage per parameter is defined as the ratio of the number of subjects with at least one PCS value occurring at a post-baseline visit and the total number of subjects in the subject sample with a post-baseline measurement of the specified parameter.
- LBT002 Summary of quantitative special laboratory parameters for determination of vitamin deficiencies, for all centers/countries combined, using default summary statistics. At each assessed visit, summary statistics will be presented as well as for the change from Baseline at each post-baseline visit.
- LBT003 The incidence of values above and below the reference range for the quantitative special laboratory parameters for determination of vitamin deficiencies will be presented. The percentage per parameter is defined as the ratio of the number of subjects with at least one value above (below) the reference range at a post-baseline visit and the total number of subjects in the subject sample with a post-baseline measurement of the specified parameter.

The laboratory test data will be presented in subject data listings as follows:

- LBL001 Hematology laboratory test data will be presented by-subject and within-subject by sample collection date and laboratory test, including the relevant reference ranges.
- LBL002 Chemistry laboratory test data will be presented by-subject and within-subject by sample collection date and laboratory test, including the relevant reference ranges.
- LBL003 Urinalysis laboratory test data will be presented by-subject and within-subject by sample collection date and laboratory test, including the relevant reference ranges.
- LBL004 Laboratory test data will be presented by-subject and within-subject by laboratory test. PCS values will be identified and only subjects with one or more PCS values for the laboratory test will be presented.

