AET006	14.3__1.2.4.9	Number and Percent of Subjects with Treatment-Emergent Adverse Events of Special Interest Related to Weight Loss SAFETY SAMPLE – US SUBSET
AET006	14.3__1.2.4.10	Number and Percent of Subjects with Treatment-Emergent Adverse Events of Special Interest Related to Cardiovascular Fatalities SAFETY SAMPLE – US SUBSET
AET006	14.3__1.2.4.11	Number and Percent of Subjects with Treatment-Emergent Adverse Events of Special Interest Related to Aspiration SAFETY SAMPLE – US SUBSET
AEL003	14.3__2.1	Listing of Subject Deaths SAFETY SAMPLE
AEL004	14.3__2.2	Listing of Serious Adverse Events SAFETY SAMPLE
AEL005	14.3__2.3	Listing of Adverse Events Leading to Study Termination SAFETY SAMPLE
AEL006	14.3__2.4	Listing of Adverse Events of Special Interest Related to Procedure and Device SAFETY SAMPLE
AEL006	14.3__2.5	Listing of Adverse Events of Special Interest Related to Polyneuropathy SAFETY SAMPLE
AEL006	14.3__2.6	Listing of Adverse Events of Special Interest Related to Weight Loss SAFETY SAMPLE
AEL006	14.3__2.7	Listing of Adverse Events of Special Interest Related to Cardiovascular Fatalities SAFETY SAMPLE
AEL006	14.3__2.8	Listing of Adverse Events of Special Interest Related to Aspiration SAFETY SAMPLE
LBT001	14.3__4.1.1	Number and Percentage of Subjects with Potentially Clinically Significant Hematology Laboratory Parameters SAFETY SAMPLE
LBL002	14.3__4.1.2	Listing of Potentially Clinically Significant Hematology Laboratory Parameters SAFETY SAMPLE
LBT001	14.3__4.2.1	Number and Percentage of Subjects with Potentially Clinically Significant Chemistry Laboratory Parameters SAFETY SAMPLE
LBL002	14.3__4.2.2	Listing of Potentially Clinically Significant Chemistry Laboratory Parameters SAFETY SAMPLE
LBT002	14.3__4.3.1	Summary of Quantitative Special Laboratory Parameters for Determination of Vitamin Deficiency SAFETY SAMPLE

SAP Table Code	Table Number	Table Title
LBT003	14.3__4.3.2	Number and Percent of Subjects with Quantitative Special Laboratory Parameters for Determination of Vitamin Deficiency Outside of the Reference Range SAFETY SAMPLE
LBT002	14.3__4.4.1	Summary of Quantitative Special Laboratory Parameters for Determination of Vitamin Deficiency SAFETY SAMPLE – NARROW POLYNEUROPATHY SUBSET
LBT003	14.3__4.4.2	Number and Percent of Subjects with Quantitative Special Laboratory Parameters for Determination of Vitamin Deficiency Outside of the Reference Range SAFETY SAMPLE – NARROW POLYNEUROPATHY SUBSET

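### The SAP sets out to evaluate an association between polyneuropathy and vitamin deficiency, but the analyses named for it cover cases only and are not aligned to event onset, so the output is descriptive

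*SAP*

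**What the plan says.** SAP 8.1.1 (Subject Samples) gives the purpose as "To evaluate the association between polyneuropathy events and vitamin deficiencies". For it, "additional analyses will be completed for the subset of subjects who experienced a TEAE coded to either the Standardized MedDRA Query" of peripheral neuropathy or Guillain-Barre syndrome, narrow search in both. This is the Narrow Polyneuropathy Subset. No complementary set is defined.

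SAP 12.2 lists four outputs for the subset:

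- Table 14.3__4.4.1 (LBT002): "Summary of Quantitative Special Laboratory Parameters for Determination of Vitamin Deficiency SAFETY SAMPLE – NARROW POLYNEUROPATHY SUBSET".
- Table 14.3__4.4.2 (LBT003): subjects outside the reference range.
- Listing 14.3__4.4.3: chemistry determinations.
- Listing 14.1__1.4.4: concomitant medication.

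The two tables are also planned for the full Safety sample, as 14.3__4.3.1 and 14.3__4.3.2, the latter titled "Number and Percent of Subjects with Quantitative Special Laboratory Parameters for Determination of Vitamin Deficiency Outside of the Reference Range SAFETY SAMPLE".

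SAP 9.11.2 defines them. For LBT002: "At each assessed visit, summary statistics will be presented as well as for the change from Baseline at each post-baseline visit". For LBT003, the percentage is "the ratio of the number of subjects with at least one value above (below) the reference range at a post-baseline visit" over "the total number of subjects in the subject sample with a post-baseline measurement of the specified parameter". Neither definition refers to event onset, and the section names no difference, ratio or test.

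SAP 8.5.2 says the special tests entered the schedule with Protocol Amendment 2.

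**The concern.** An association is a contrast. It needs subjects with and without the event, and to be informative about vitamin status as a possible precursor it needs values that precede the event. The analyses named for this aim have neither. A percentage with low vitamin B12 among cases has no reference point, and a low value recorded after onset says nothing about what came first.

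Polyneuropathy is an adverse event of special interest in Protocol 12.1.4 and SAP 8.5.1, and the special laboratory tests are part of the secondary safety objective (Protocol 6.2, SAP 7.2). The study report is likely to comment on this question, and the planned tables could be read in either direction without support.

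**Working it through.** The documents state no rate, effect size or precision for this analysis, so there is no figure of the plan's own to reproduce. The check is structural, followed by illustrations on assumed rates.

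**1. What a reader can compare.** The only reference is the Safety sample, which contains the cases. Let f be the share of cases, c the proportion deficient among cases and n the proportion among non-cases.

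- Whole sample: w = f·c + (1 − f)·n
- Difference seen: c − w = (1 − f)(c − n)

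Assume f = 0.15, c = 0.60, n = 0.30. Then w = 0.09 + 0.255 = 0.345.

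- Cases against whole sample: difference 0.255; odds ratio (0.60/0.40)/(0.345/0.655) = 2.85
- Cases against non-cases: difference 0.30; odds ratio (0.60/0.40)/(0.30/0.70) = 3.50

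With f from 0.05 to 0.20, the first odds ratio runs from 3.26 down to 2.67. This is attenuation, not loss of the signal.

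**2. What subtraction recovers.** The subset lies within the Safety sample and LBT003 uses the same denominator rule in both, so non-case counts are Safety minus subset. For example, with 275 subjects, 55 cases (33 low) and 99 low overall, non-cases are 66 of 220 (30%) and the odds ratio is (33 × 154)/(66 × 22) = 3.5. For LBT002, a mean can be back-calculated from n and the two means, but medians, minima and maxima cannot.

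**3. Test count in LBT003.** With chance p of an out-of-range value per test and independent tests, P(ever out of range) = 1 − (1 − p)^k.

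| p | k = 2 | k = 4 | k = 8 | k = 14 |
|---|---|---|---|---|
| 2.5% | 4.9% | 9.6% | 18.3% | 29.8% |
| 5% | 9.8% | 18.5% | 33.7% | 51.2% |
| 10% | 19.0% | 34.4% | 57.0% | 77.1% |

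SAP Table 2 has 14 post-baseline windows (Month 6 to Month 84), hence k up to 14. Correlation between repeat values in one subject would flatten these figures.

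**4. Test count and case status together, with no association.** Both an event and an out-of-range value become more likely with time on study. Assume k is uniform on 1 to 14, event risk h per interval is 1% or 3%, and the two processes are independent given k. Then P(ever out of range | case) = Σ[1 − (1 − h)^k][1 − (1 − p)^k] / Σ[1 − (1 − h)^k], and likewise for non-cases with (1 − h)^k as the weight.

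- p = 5%: about 38% of cases against 29–30% of non-cases; odds ratio 1.43 to 1.49
- p = 10%: about 61% against 48–50%; odds ratio 1.60 to 1.67

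The contrast recovered in step 2 can therefore show an association where there is none. This bias is upward, whereas the dilution in step 1 pulls a true difference down.

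**5. Order of events.** If onset is uniform over k intervals and unrelated to the laboratory values, the share of ever-low cases whose first low value falls after onset is Σ p(1 − p)^(j−1)(j/k) / [1 − (1 − p)^k], summed over j = 1 to k. For p of 5% or 10% and k of 4, 8 or 14 this is 42% to 61%. LBT003 does not distinguish these cases.

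**The case against.** A reader might infer that the plan cannot show an association at all, that every value is taken without regard to time, and that timing and supplementation are out of reach. The documents do not support any of these.

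- The two tables exist for the Safety sample, so a crude contrast is available: diluted if read directly, undiluted for LBT003 after subtraction.
- The any-time criticism applies to LBT003 only. LBT002 is by visit with change from baseline, and SAP 6.4.8 keeps one assessment per window, so it does not grow with the number of tests.
- Dated listings are planned: chemistry by collection date and medication by start date for the subset, adverse events by start date (AEL001), and a polyneuropathy event listing (14.3__2.5). They permit case-by-case review of order and of recorded supplements, although the title of the chemistry listing does not name the special tests.

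It is also fair that the association is not a listed objective in Protocol 6.2 or SAP 7.2, that the SAP calls these analyses additional, and that Protocol 13.4 gives no alpha. A hypothesis test is not owed.

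What remains is that neither subtraction nor listings supply a comparison aligned to onset or balanced for number of tests, and no listing for the subset covers non-cases. A descriptive study still needs a comparator before its output can speak to association.

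**Conclusion.** The point holds as a mismatch between a stated aim and the output planned for it. The named analyses are in cases only; the Safety-sample tables give a comparator that includes the cases; LBT003 mixes values before and after onset and depends on the number of tests; LBT002 is timed to study visits, not to onset. The result is descriptive and does not evaluate the association.

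The size cannot be fixed from the documents. Under the assumed rates, dilution turns an odds ratio of 3.5 into 2.7 to 3.3 for a case share of 20% down to 5%, and unequal follow-up alone gives about 1.4 to 1.7 with no association. These figures show direction and plausibility, not expected results. The point concerns a safety question of special interest, not the study's primary objective.

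**What to change.** A cheap improvement, using data already collected:

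1. Add a column for subjects with no narrow polyneuropathy event to Tables 14.3__4.4.1 and 14.3__4.4.2.
2. Add one table giving, for cases, the last special-laboratory value before event onset and, for comparison, the value in the same visit window in non-cases who are still on study and event-free. Report the difference in proportions out of range with a 95% confidence interval labelled descriptive. One value per subject at a comparable time removes the test-count and after-onset problems. The SAP should state how a non-case who qualifies in several windows is used.
3. List separately the cases with no pre-onset value, for example those with onset before Amendment 2 testing.

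The cost is more than extra columns: a derivation from onset date and a visit-matching rule must be specified and programmed. Some cases drop out of the timed comparison. With six-monthly testing the pre-onset value may be months old. Some onset dates are imputed towards the earliest possible date (SAP 8.5.1), which can misplace a value relative to onset.

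If the sponsor does not want this work, the minimum is to reword the sentence in SAP 8.1.1 so that it promises a description of vitamin values in subjects with polyneuropathy and not an evaluation of association.

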8.1.2 Subgroups

Subgroups to evaluate the robustness of efficacy observations will be based on the following:

- the study in which the subject received their first LCIG infusion (3001/2, 3003, 3004)
- troublesome dyskinesia at initial LCIG infusion (< 1 hour, > 1 hour as recorded on the PD Diary)
- total daily levodopa dose at initial LCIG infusion (< 1250 mg/day, > 1250 mg/day), and
- levodopa monotherapy in Study S187.3.005 (yes, no)

To evaluate the robustness of observations, the change in total daily levodopa dose will be evaluated after grouping subjects by the study in which they received their first LCIG infusion.

Subgroups defined for exploratory analyses of safety will include gender, age category (< 65, ≥ 65 years), duration of Parkinson's disease (< 10 years, ≥ 10 years) and country.

Due to the similarity in study design, Studies 3001 and 3002 will be combined and considered a single study (Study 3001/3002) for the subgroup analysis based on the study in which the subject received their first LCIG infusion.

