6.4.4 Initial LCIG Infusion

Subjects enrolled in Study 3005 had their first LCIG infusion in the same study as their initial PEG-J placement (Studies 3001, 3002 or 3004) except for subjects who received levodopa-carbidopa capsules and placebo gel in Study 3001 or Study 3002. These subjects had their first LCIG infusion in Study 3003. To allow the overall duration of LCIG exposure to be summarized for each subject in Study 3005, the date of initial LCIG infusion will be retrieved from the relevant study database.

For US subjects who completed Daily Dosing Diaries in Study 3005 following Amendment 4, the total daily levodopa dose at the end of the subject's initial LCIG titration period will be retrieved from the relevant database to allow the change in dose from initial titration to final Study 3005 visit to be determined.

To provide context for changes in efficacy measures observed during Study 3005, the respective change observed between initial LCIG infusion and Study 3005 final visit will be determined and summarized. For subjects who completed efficacy assessments in Study 3005, their baseline value from the study in which they had their first LCIG infusion will be retrieved from the relevant database and considered their value at initial LCIG infusion.

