8.4 Efficacy Analysis Variables

The original Protocol included the following efficacy measures:

- Parkinson's Disease Diary⁴
- Parkinson's Disease Questionnaire (PDQ-39)
- Clinical Global Impression – Improvement (CGI-I)

These measures were removed from the schedule of assessments with Protocol Amendment 1. With Protocol Amendment 4, the following measures were added to the schedule of assessments for subjects enrolled at US sites:

- Parkinson's Disease Diary
- Unified Parkinson's Disease Rating Scale (UPDRS)
- Parkinson's Disease Questionnaire (PDQ-39)

The change in each efficacy measure from 3005 baseline to 3005 final visit will be determined and summarized. To provide context, the change in each efficacy measure from initial LCIG infusion to 3005 final visit will also be determined and summarized.

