6. Valid symptom diary days (at least 12 awake hours) will be used to compute the average daily normalized "off" time. For post-baseline visits, the valid symptom diary day must be within 7 days of the clinic visit but not on or after the day of the clinic visit. If more than 3 valid symptom diary days are available, the 3 days closest to the clinic visit will be used.
7. If only 2 valid symptom diary days are available prior to a clinic visit, data from the 2 days will be used to calculate the average daily normalized "off" time.
8. If only one valid symptom diary day is available the average daily from the previous visit will be averaged with the daily normalized "off" time from the one valid diary day.
9. Subjects that do not have any valid symptom diary days for a visit or who are completely missing a visit will have the average daily normalized "off" time set to missing for that visit.

The change from baseline in average daily normalized "on" time with troublesome dyskinesia, normalized "on" time with non-troublesome dyskinesia, and normalized "on" time without dyskinesia will be calculated for each subject using the 3 diary days prior to the visit and the same strategy employed for the calculation of normalized "off" time. Normalized "on" time without troublesome dyskinesia will be calculated for each PD Diary as the sum of normalized "on" time without dyskinesia and normalized "on" time with non-troublesome dyskinesia.

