9.9 Efficacy Analyses

Subject Samples:	Tables	Efficacy Sample and US Subset
	Listings	All subject consented
	Figures	Not applicable
Subgroups:		First LCIG infusion study (3001/3002, 3003 or 3004), troublesome dyskinesia at initial LCIG infusion (< 1 hour, > 1 hour), dose of levodopa at initial LCIG infusion (< 1250 mg/day, > 1250 mg/day), and levodopa monotherapy during Study 3005 (yes, no)
Abbreviation:		QS

Standard Presentations

QST001 The average daily normalized "off" time will be summarized at initial LCIG infusion, at 3005 baseline and at 3005 endpoint as well as the change from initial LCIG infusion to 3005 endpoint and the change from 3005 baseline to 3005 endpoint. Descriptive statistics (including n, mean, minimum, maximum and 95% confidence interval) will be calculated.

Statistical tests for within group changes from initial LCIG infusion and from 3005 baseline will be implemented using PROC UNIVARIATE.

For the UNIVARIATE the following SAS[®] code will be used:

*PROC UNIVARIATE data = <SAS[®]-dataset> cibasic alpha = 0.05;
VAR OFFTIME;*

RUN;

The same methods defined above for average daily normalized "off" time will also be used to analyze the following assessments:

1. Change in average daily normalized "on" time without troublesome dyskinesia
2. Change in average daily normalized "on" time with troublesome dyskinesia
3. Change in average daily normalized "on" time with non-troublesome dyskinesia
4. Change in average daily normalized "on" time without dyskinesia
5. Change in the UPDRS total score, subscores of Parts I – IV and Part IV Questions 32, 33 and 34 (Dyskinesia items)
6. Change in the PDQ-39 summary index and each domain score

Variables derived from the PD Diary and PDQ-39 will be summarized for the Efficacy sample and the US subset of the Efficacy sample.

Variables derived from the UPDRS will be summarized for the US subset of the Efficacy sample.

QST002 The change from initial LCIG infusion to 3005 endpoint and from 3005 baseline to 3005 endpoint will be summarized by subgroup in the Efficacy sample – US Subset for the PD Diary variables.

QST003 The CGI score at 3005 endpoint will be summarized using the appropriate default summary statistics for the Efficacy sample.

Subject data listings will include:

- QSL001 A listing of Parkinson's Disease Diary data by-subject and within-subject by visit will be presented.
- QSL002 A listing of CGI-I scores by-subject and within-subject by visit will be presented.

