10.0 Changes to Planned Analyses

10.1 Changes to the Analysis as Laid Down in the Protocol and Amendments

The protocol statistical methods (Section 6.2 and Section 13.3) stated that for the analysis of change from baseline in efficacy measures, each subject's baseline will be their baseline measure in the first LCIG study in which they participated (e.g., Studies S187.3.001, S187.3.002 or S187.3.004). To focus the analysis on the maintenance of efficacy during participation in Study 3005, each subject's baseline value for the analysis of change from

baseline in efficacy measures will be the final value in the preceding open-label study. To provide context, the change in each efficacy measure from initial LCIG infusion to 3005 endpoint will also be determined and summarized.

Protocol Section 12.1.4 identifies the following as adverse events of special interest:

- Risks of PEG-J insertion
- Long-term complications of PEG-J
- Device-associated gastrointestinal disorders during long-term therapy

For consistency with current practice throughout the LCIG development program, these 3 categories have been combined into a single category of procedure and device associated events (Duodopa product specific CMQ).

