QST002	14.2__2.5.2	Change in Average Daily "On" Time Without Troublesome Dyskinesia Based on the Parkinson's Disease Symptom Diary in Subgroups Determined by Troublesome Dyskinesia at Initial LCIG Infusion EFFICACY SAMPLE – US SUBSET
QST002	14.2__2.5.3	Change in Average Daily "On" Time With Troublesome Dyskinesia Based on the Parkinson's Disease Symptom Diary in Subgroups Determined by Troublesome Dyskinesia at Initial LCIG Infusion EFFICACY SAMPLE – US SUBSET
QST002	14.2__2.5.4	Change in Average Daily "On" Time With Non Troublesome Dyskinesia Based on the Parkinson's Disease Symptom Diary in Subgroups Determined by Troublesome Dyskinesia at Initial LCIG Infusion EFFICACY SAMPLE – US SUBSET
QST002	14.2__2.5.5	Change in Average Daily "On" Time Without Dyskinesia Based on the Parkinson's Disease Symptom Diary in Subgroups Determined by Troublesome Dyskinesia at Initial LCIG Infusion EFFICACY SAMPLE – US SUBSET

SAP Table Code	Table Number	Table Title
QST002	14.2__2.6.1	Change in Average Daily "Off" Time Based on the Parkinson's Disease Symptom Diary in Subgroups Determined by Levodopa Monotherapy in Study S187.3.005 EFFICACY SAMPLE – US SUBSET
QST002	14.2__2.6.2	Change in Average Daily "On" Time Without Troublesome Dyskinesia Based on the Parkinson's Disease Symptom Diary in Subgroups Determined by Levodopa Monotherapy in Study S187.3.005 EFFICACY SAMPLE – US SUBSET
QST002	14.2__2.6.3	Change in Average Daily "On" Time With Troublesome Dyskinesia Based on the Parkinson's Disease Symptom Diary in Subgroups Determined by Levodopa Monotherapy in Study S187.3.005 EFFICACY SAMPLE – US SUBSET
QST002	14.2__2.6.4	Change in Average Daily "On" Time With Non Troublesome Dyskinesia Based on the Parkinson's Disease Symptom Diary in Subgroups Determined by Levodopa Monotherapy in Study S187.3.005 EFFICACY SAMPLE – US SUBSET
QST002	14.2__2.6.5	Change in Average Daily "On" Time Without Dyskinesia Based on the Parkinson's Disease Symptom Diary in Subgroups Determined by Levodopa Monotherapy in Study S187.3.005 EFFICACY SAMPLE – US SUBSET
QST002	14.2__2.7.1	Change in Average Daily "Off" Time Based on the Parkinson's Disease Symptom Diary in Subgroups Determined by Levodopa Dose at Initial LCIG Infusion EFFICACY SAMPLE – US SUBSET
QST002	14.2__2.7.2	Change in Average Daily "On" Time Without Troublesome Dyskinesia Based on the Parkinson's Disease Symptom Diary in Subgroups Determined by Levodopa Dose at Initial LCIG Infusion EFFICACY SAMPLE – US SUBSET

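### Table 14.2__2.5.3 measures change in troublesome dyskinesia from the same initial-infusion value that defines its subgroups, so part of any subgroup difference in that contrast is regression to the mean

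*SAP*

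**What the plan says.** SAP 8.1.2 defines four factors for checking the robustness of the efficacy findings. One is "troublesome dyskinesia at initial LCIG infusion (< 1 hour, > 1 hour as recorded on the PD Diary". SAP 6.4.4 fixes what the value at initial infusion is: each subject's "baseline value from the study in which they had their first LCIG infusion will be retrieved from the relevant database" and counts as the value at initial LCIG infusion.

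SAP 9.9 (QST002) then states, for the PD Diary variables in the US subset of the Efficacy sample: "The change from initial LCIG infusion to 3005 endpoint and from 3005 baseline to 3005 endpoint will be summarized by subgroup". SAP 12.2 lists five such tables, 14.2__2.5.1 to 14.2__2.5.5, one per diary variable, each titled "in Subgroups Determined by Troublesome Dyskinesia at Initial LCIG Infusion". Table 14.2__2.5.3 is the one whose outcome is On time with troublesome dyskinesia.

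The two changes do not have equal standing. SAP 10.1 says that the "baseline in efficacy measures will be the final value in the preceding open-label study". The other change is secondary in SAP 8.4: "To provide context, the change in each efficacy measure from initial LCIG infusion to 3005 final visit will also be determined and summarized".

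Neither document mentions regression to the mean or plans an adjustment or note for it.

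**The concern.** In the first contrast of Table 14.2__2.5.3 one measurement does two jobs: it decides which subgroup a subject joins, and it is subtracted to form the change. Diary values are noisy. SAP 8.4.1 averages few days: "If more than 3 valid symptom diary days are available, the 3 days closest to the clinic visit will be used". Subjects placed above 1 hour therefore include some caught on unusually bad days, who tend to fall on re-measurement. Those placed below 1 hour include some caught on unusually good days, who tend to rise.

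A floor adds to this. A subject who starts below 1 hour can lose less than 1 hour of troublesome dyskinesia whatever the treatment does, while a subject who starts well above 1 hour has more room to improve.

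The study has a single arm, so no comparison group regresses by the same amount. A reader who uses the table to judge robustness could credit LCIG with a benefit confined to subjects with more dyskinesia, or suspect harm in those with little, when selection alone accounts for some of the difference.

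**Working it through.** The plan states no sample size, power or effect size for these subgroups, so there is no planned figure to reproduce. The check has three steps.

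**1. Direction.** Let p be a group's share of subjects and D its mean change. If the overall mean change is zero, p_low × D_low + p_high × D_high = 0, so the two mean changes have opposite signs unless both are zero. Under a linear stationary model with mean mu and correlation r between the initial and endpoint values:

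E[X_end − X_init | X_init] = −(1 − r)(X_init − mu).

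For any r below 1 this is negative above the mean and positive below it.

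**2. Size from initial infusion to 3005 endpoint.** None of these inputs is in the documents; all are assumptions:

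- Margin: zero-inflated gamma, mean 1.0 to 2.0 h, 20% to 40% zeros, positive part with coefficient of variation 1, capped at 16 h.
- Dependence: Gaussian copula across three time points, correlation 0.3 to 0.9. The resulting correlations in hours are about 0.23 to 0.88.
- No true change; 300,000 simulated subjects per scenario.

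| Copula correlation | < 1 h group | > 1 h group |
|---|---|---|
| 0.3 | +0.60 to +1.19 h | −0.96 to −1.43 h |
| 0.5 | +0.45 to +0.83 h | −0.68 to −1.03 h |
| 0.7 | +0.27 to +0.49 h | −0.41 to −0.64 h |
| 0.9 | +0.10 to +0.16 h | −0.13 to −0.23 h |

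Check against the identity (40% zeros, mean 1.5 h, correlation 0.7, low share 0.60): 0.60 × 0.43 − 0.40 × 0.64 = 0.258 − 0.256 ≈ 0. The spurious difference between groups in that scenario is −0.64 − 0.43 = −1.07 h.

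The number of US subjects is not given. Taking 50, or 28/70 × 275 = 110 if subjects are spread evenly over centers, with mean 1.5 h, 30% zeros and correlation 0.3 to 0.7, a single simulated trial shows the low group up and the high group down in 86% to 98% of runs (N = 50) or 94% to 99.7% (N = 110).

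**3. The other contrast, 3005 baseline to 3005 endpoint, same subgroups.** Under the same linear model:

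E[X_end − X_base | X_init] = (r_init,end − r_init,base)(X_init − mu).

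- Constant correlation: the bracket is zero. Simulation gives 0.00 ± 0.01 h in both groups.
- Decaying correlation (0.6 from initial to 3005 baseline, 0.4 from initial to endpoint): a residual remains, +0.16 to +0.35 h (low) and −0.28 to −0.39 h (high). The linear model puts it at (0.6 − 0.4)/(1 − 0.4) = one third of the initial-infusion artefact. The simulation agrees: with 40% zeros and mean 1.5 h, 0.27 against 0.83 h in the low group and −0.39 against −1.24 h in the high group.

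**The case against.** The strongest reply is that the plan already has the better contrast. The 3005-baseline change appears in the same tables, is the main one under SAP 10.1, and does not start from the classifying value; the initial-infusion change is offered only as context. These are descriptive US-subset tables for one factor of four, in a study whose protocol names no primary outcome measure (11.5) and no alpha level (13.4). No test between subgroups is planned. QST002 speaks only of summaries; the within-group tests are written under QST001. All of this stands, and it limits the severity. It does not remove the artefact from the contrast that is still planned.

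Three stronger readings are tempting and not supported:

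- *All five diary tables share the defect.* The classifier is the outcome only in 14.2__2.5.3. SAP 8.4.1 scales the waking states to 16 hours, so the other four are linked to it, but that constraint does not say how an offsetting change divides among them. On time without troublesome dyskinesia would tend to move the opposite way; the sign for Off time cannot be derived from the documents.
- *The table is bound to show improvement in one group and worsening in the other.* That pattern is expected only when the overall mean change is near zero. A true overall change adds to the artefact and can hide the opposite signs, although the distortion between groups remains.
- *The 3005-baseline change is entirely clean.* It is clean only under constant correlation.

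**Conclusion.** The point holds for one contrast in one table: the change from initial LCIG infusion to 3005 endpoint in Table 14.2__2.5.3. There the same diary value classifies subjects and starts the change, so part of any difference between the < 1 hour and > 1 hour groups comes from selection, and the floor limits what the low group can show. The direction of the distortion follows from the SAP's definitions and any correlation below 1. Its size does not: about +0.1 to +1.2 h (low) and −0.1 to −1.4 h (high) rests on assumed means, zero fractions and correlations, with no true change. The overall QST001 results are untouched, and the other three subgroup factors are not split on a diary value. Severity is minor.

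**What to change.** - **Table 14.2__2.5.3:** for this factor report only the change from 3005 baseline to 3005 endpoint and drop the change from initial LCIG infusion. The latter stays in the overall QST001 table.
- **Subgroup means:** do not show initial-infusion and endpoint means side by side in these subgroups without a footnote, because subtraction would restore the dropped change. The footnote should say that subjects were classified on the initial value and that regression to the mean is expected.
- **Tables 14.2__2.5.1, .2, .4 and .5:** keep the initial-infusion change and add the same footnote.

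The cost is a wording change to QST002, one block removed from one table and footnotes in the others. One contextual figure is lost for one subgroup factor. The retained contrast may still carry a smaller residual if correlation decays over time.
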